5.2. General Methods

The efficacy of study medication is obtained via comparison of pre- and post PF-06838435 infusion measure collected for each participant. For comparisons of ABR, AIR, and FIX consumption, pre PF-06838435 data are from the Pre-Infusion Period consisting of data collected in the lead-in study C0371004 and during the period prior to study drug infusion in C0371002. For comparisons of safety evaluation and other efficacy endpoints, pre PF-06838435 data will be from baseline in C0371002, which is defined in Section 3 for each endpoint.

Visit windows may be developed for specific data points (i.e., FIX:C, ABR, AIR, annualized FIX consumption and AE) in reference of SoA, so the data may be summarized by visit. Each yearly observation period used for analysis will be 365 days, beginning with PF-06838435 infusion where days is calculated relative to the date of PF-06838435 infusion in C0371002 +1 day. Any visit dates beyond 2190 days will also be included in Year 6 for analysis.

Year	
1	Date of PF-06838435 infusion < Year $1 \le 365$ days
2	$365 \text{ days} < \text{Year } 2 \le 730 \text{ days}$
3	730 days < Year 3 \leq 1095 days
4	$1095 \text{ days} < \text{Year } 4 \le 1460 \text{ days}$
5	$1460 \text{ days} < \text{Year } 5 \le 1825 \text{ days}$
6	1825 days < Year 6

For AE, the following visit windows will be applied:

Further details of windowing will be described separately for each endpoint in Section 3, as applicable.

For ABR_{treat}, AIR, ABR_{total}, annualized FIX consumption, and ABR_{total} of specific bleed types, the primary analysis period will include all assessments from Week 12 (Day 82) to Month 15 (Day 469). And Year 2 will include all assessments from Day 470 to Day 730. Year 3 to Year 6 have the same visit windows as listed above for AE.

For FIX:C, visit window will be considered when deriving yearly intervals:

Year	
Week 12 to	82 days < Week 12 to Month $15 \le 469$ days
Month 15	

2	470 days < Year $2 \le 744$ days (Week 104+2 weeks of visit window, Day
	744)
3	745 days < Year $3 \le 1109$ days (Week 156+2 weeks of visit window, Day 1109)
4	1110 days < Year $4 \le 1481$ days (Week 208+3 weeks of visit window, Day 1481)
5	1482 days < Year $5 \le 1846$ days (Week 260+3 weeks of visit window, Day 1846)
6	1847 days < Year 6

For participants in whom the corticosteroid treatment are initiated, FIX:C and ABR_{total} will be calculated for the following periods:

Periods	Derivation of time period (Corticosteroid is initiated before Week 12 [Day 82])	Derivation of time period (Corticosteroid is initiated after Week 12 [Day 82])
prior to corticosteroid initiation	Not calculatable	date of corticosteroid initiation – Day 82
during corticosteroid treatment	date of stop of corticosteroid – Day 82 +1 *if corticosteroid is stopped before Day 82, then this time period will not be calculated.	date of stop of corticosteroid – date of initiation of corticosteroid +1
post-corticosteroid treatment	Month 15 or last contact date if has not reached Month 15 – date of stop of corticosteroid (or Day 82, whichever is later)	Month 15 or last contact date if has not reached Month 15 – date of stop of corticosteroid
overall time period	Month 15 (or last contact date if has not reached Month 15) – Day 82 +1	Month 15 (or last contact date if has not reached Month 15) – Day 82 +1

*days without corticosteroid treatment will be excluded from the derivation of corticosteroid treatment period.

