2. INTRODUCTION

PF-06838435 (generic name: fidanacogene elaparvovec; formerly known as SPK 9001 or rAAV Spark100-hFIX-Padua, which is also referred to as Spark100-hFIX-R338L) is an adeno-associated viral (AAV) vector designed to drive expression of the human factor IX-R338L (hFIX-R338L) transgene and raise the circulating levels of factor IX (FIX:C).

C0371002 is a single-arm pivotal phase 3 study designed to evaluate clinical efficacy and safety of PF-06838435 in adult male participants with moderately severe or severe

hemophilia B (FIX:C $\leq 2\%$ or ≤ 2 international units per deciliter [IU/dL]) for the study duration of 6 years after a single administration of the study treatment. The primary efficacy endpoint of C0371002 is annualized bleeding rate (ABR) for total bleeds (treated and untreated) (referred to as ABR_{total} hereafter in this document) from Week 12 [Week 12 ± 2 days of visit window, Day 82] to Month 15 [Week 65 ±2 weeks of visit window, Day 469]. The study will enroll eligible participants who have completed at least 6 months of routine prophylaxis in the C0371004 study. The bleeding and factor IX (FIX) infusion data prior to PF-06838435 infusion (consisting of data collected in C0371004 and during the period prior to study drug infusion in C0371002, referred to as "Pre-Infusion Period" hereafter in this document) will serve as the control to be compared to bleeding and FIX infusion data post PF-06838435 infusion in C0371002.

This SAP provides the detailed methodology for summary and statistical analyses of the data collected in Study C0371002. This document may modify the plans outlined in the protocol; however, any major modifications of the primary endpoint definition or its analysis will also be reflected in a protocol amendment. A separate SAP will be prepared, describing the anchor-based approach for evaluating the meaningful within-patient change (MW-PC) for Haem-A-QoL, HAL and HLIQ based on Patient Global Impression of Change – Hemophilia (PGIC-H).

Any deviations from this analysis plan will be described in the Clinical Study Report.

Objectives	Endpoints
Primary	

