6.1.1.2. Supplementary Analysis

As a supportive analysis, the frequency of bleeding will also be analyzed using a repeated measures generalized linear model with negative binomial distribution and log link function. Treatment (prophylaxis, or PF-06838435) will be a class factor in the model, and participant will be a random effect. Log transformed duration of time on study will be included as an offset variable in the model. Mean percentage of reduction in ABR_{total} and its 95% CI, as well as p-value will be provided. Sample SAS code is provided in Appendix 1.2.

The following sensitivity analyses will be performed:

- 1. Comparing the ABR_{total} from Week 12 to Month 15 to the ABR_{total} collected during C0371004 , excluding pre-infusion bleeds from C0371002.
- 2. Comparing the ABR_{total} from Week 12 to Month 15 to the ABR_{total} during the most recent 6 months prior to infusion.
- 3. A "Jump to Reference" analysis will be performed to assess the impact on ABR_{total} of participants who discontinue the study prior to completing follow up (including those with FIX infusion resumption). The ABR_{total} for participants who were dosed at least 15 months prior to the data cutoff date but discontinued prior to completing 15 months of follow up will be included in the analysis with the ABR_{total} during the time period between discontinuation and Month 15 imputed based on the ABR on prior prophylaxis.
- 4. Sensitivity analysis on ABR_{total} of first 15 months post PF-06838435 infusion will be conducted.

These sensitivity analyses will be conducted on the Dosed population.

ABR_{total} Year 2 (Month 15 to Month 24), Year 3, Year 4, Year 5, and Year 6, as well as ABR_{total} through the overall follow up will be compared to ABR_{total} of FIX prophylaxis using the same statistical methods as ABR_{total} is analyzed, first to assess noninferiority with noninferiority margin 3 and then to assess superiority if noninferiority is established.

A table will be provided summarizing ABR_{total} during the following periods: prior to corticosteroid initiation, during corticosteroid treatment and post-corticosteroid treatment (Section 1.1.1) for the participants in whom corticosteroid is initiated. ABR_{total} during the overall time period (Week 12 to Month 15) for participants who do not have corticosteroid treatment will be presented side by side in the same table.

The above analysis will be conducted on Dosed population.

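### In SAP 5.2 the prior and during corticosteroid periods are not cut at Month 15, and with repeat courses the off-steroid gap days have no clear period

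*SAP*

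**What the plan says.** SAP 5.2 sets the window for ABR_total and related endpoints: "the primary analysis period will include all assessments from Week 12 (Day 82) to Month 15 (Day 469"). SAP 2 explains the upper limit as "Week 65 ±2 weeks of visit window, Day 469".

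For participants who start corticosteroids, a table in SAP 5.2 then divides that window. When the start is after Day 82:

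- *prior* is "date of corticosteroid initiation – Day 82";
- *during* is "date of stop of corticosteroid – date of initiation of corticosteroid +1";
- *post* is "Month 15 or last contact date if has not reached Month 15 – date of stop of corticosteroid";
- *overall* is "Month 15 (or last contact date if has not reached Month 15) – Day 82 +1".

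When the start is before Day 82, *prior* is not calculated, *during* counts from Day 82 to the stop date, and *post* counts from the stop date or Day 82, whichever comes later. The footnote to the table adds that "days without corticosteroid treatment will be excluded from the derivation of corticosteroid treatment period".

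The periods feed two summaries. SAP 6.1.1.2 says "A table will be provided summarizing ABR" (total bleeds) by these periods, and SAP 6.2.3.2 plans the same for FIX:C. In both, participants without corticosteroids are shown alongside.

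**The concern.** The lower edge of the window is guarded and the upper edge is not. *Post* and *overall* end at Month 15, but nothing limits the initiation date in *prior* or the stop date in *during* and *post*. A course that crosses Day 469 breaks the split, and so does a first course that begins after it.

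The footnote raises a second question. It presupposes interrupted treatment and takes the off-steroid days out of *during*, but it does not say where they go. Nor does the table say whether the stop date is the first or the last.

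The period lengths matter because SAP 3.1.1 annualizes bleeds by the number of days in the period. No bleed can fall in a period of negative length, so the formula would return a zero rate for a period that the participant did not have. FIX:C has no day denominator, but the period limits decide which samples enter each geometric mean. If the rule is left open, the programmer has to settle it with open-label data already visible.

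**Working it through.** **Inputs.** The window limits come from SAP 2 and 5.2, and the formulas from the SAP 5.2 table. The dosing histories are assumed, because the documents give no frequency of late or repeat courses and no maximum gap.

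**Window.** 12 × 7 − 2 = 82 and 65 × 7 + 14 = 469, which reproduces the plan's Day 82 and Day 469. Overall = 469 − 82 + 1 = 388 days.

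**Single courses, formulas as printed**

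| Course | prior | during | post | sum |
|---|---|---|---|---|
| Day 100-155 | 100 − 82 = 18 | 155 − 100 + 1 = 56 | 469 − 155 = 314 | 388 |
| Day 460-520 | 460 − 82 = 378 | 520 − 460 + 1 = 61 | 469 − 520 = −51 | 388 |
| Day 500-555 | 500 − 82 = 418 | 555 − 500 + 1 = 56 | 469 − 555 = −86 | 388 |
| Day 60-480 | not calculated | 480 − 82 + 1 = 399 | 469 − 480 = −11 | 388 |

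The first row shows that the formulas work for a course inside the window. In the other rows the total is still 388, but the separate periods are wrong. For Day 460-520 only 469 − 460 + 1 = 10 of the 61 *during* days lie in the window. Capping at Day 469 gives 378/10/0 for that course and 388 *during* days for Day 60-480. The Day 500 participant has no corticosteroid day in the window.

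**When a course overruns.** Protocol Table 1 recommends an eight-week (56-day) oral course, used here only as an illustration. A start on day S stops on S + 55, which exceeds 469 when S is 415 or later.

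**Repeat courses, stop date read as the last stop**

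- Day 100-160 and 300-360: prior 18; during 61 + 61 = 122; post 469 − 360 = 109. The sum is 249, so 388 − 249 = 139 days (35.8%) are in no period. This is the gap, Day 161 to 299.
- Day 40-75 and 200-255: during 255 − 82 + 1 = 174, less the 118 off-steroid days from Day 82 to 199, leaves 56; post 469 − 255 = 214. The sum is 270, so 118 days (30.4%) are in no period.
- Day 83-138 and 414-469: 1 + 112 + 0 = 113, so 275 days (70.9%) are in no period.

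**Repeat courses, stop date read as the first stop.** For Day 100-160 and 300-360: 18 + 61 + (469 − 160 = 309) = 388. All days are placed, but the 309 *post* days contain the 61 on-steroid days of the second course, the 139 gap days and 109 days after the last stop (61 + 139 + 109 = 309).

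**Smaller edges.** A start exactly on Day 82 fits neither column of the table. A course that ends before Day 82 gives post = 469 − 82 = 387, one day short of 388.

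**The case against.** The best defence is that the table should be read with its surroundings. SAP 5 limits primary-analysis data to 15 months after infusion, SAP 5.2 states the Day 82 to 469 window, and *post* and *overall* name Month 15. A careful programmer would cap the dates and treat a Day 500 start as outside the analysis. It is therefore too broad to infer that the table has no Month 15 limit at all. What remains is that the printed formulas for *prior* and *during* give results that contradict the stated window.

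On gaps, the text is ambiguous, and the first-stop reading leaves no day unassigned. That reading fits the footnote poorly, because a single uninterrupted course has no off-steroid days to remove. The related definition of total time on corticosteroids in SAP 6.6.2 is incomplete in the text available to me, probably from PDF conversion, so it cannot settle the matter.

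It is also fair to say that late or repeat courses may be few. Protocol 2.2.2 reports two of ten Phase 1/2 patients with liver enzyme increases that resolved with short-term prednisone. However, Protocol 8.3.8 covers decisions beyond 120 days and leaves the regimen flexible, and the Year 2 to Year 6 schedule provides sampling for further courses.

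**Conclusion.** The defect is real but small. As printed, a course that passes Day 469 gives negative *post* days and *during* days outside the window, and a first course after Day 469 gives a *prior* period longer than 388 days. With repeat courses, either the gap days belong to no period (last stop) or on-steroid days count as *post* (first stop). All the sizes rest on assumed dosing histories.

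Three stronger readings are not supported:

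- **A fixed upper limit on the lost time, such as a third of the window.** The loss equals the gap length, and the documents set no maximum gap.
- **An inflated on-steroid bleeding rate.** For Day 100-160 and 300-360 a factor of 261/122 = 2.1 would need a constant bleed rate, with gap bleeds kept while gap days are removed. The SAP does not say this. Where SAP 3.1.1 excludes time after prophylaxis resumption, it excludes the bleeds with it.
- **A threat to the efficacy conclusions.** The summaries by corticosteroid period are descriptive and outside the testing sequence in SAP 5.1. The overall row, the primary ABR_total comparison and the gatekeeping tests do not use these formulas.

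**What to change.** Replace the period formulas in SAP 5.2 with a day-level rule:

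1. Cap initiation and stop dates at the earlier of Day 469 or last contact.
2. Treat participants whose first corticosteroid is after Day 469 as having none in this window, and show them in the no-corticosteroid column.
3. Assign each eligible day from Day 82 to one state: before first corticosteroid, on corticosteroid, or off corticosteroid after the first course. Bleeds and FIX:C samples take the state of their date. Gap days between courses may be shown separately from days after the last course.
4. Keep the SAP 3.1.1 exclusion of time and bleeds after FIX prophylaxis resumption, and the SAP 3.2.3 exclusion of FIX:C samples taken soon after exogenous FIX.

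The rule also closes the two one-day edges at Day 82. The cost is SAP wording and a simple derivation, with no new data.

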5.2.1. Analyses for Binary Endpoints

Descriptive statistics of binary data will include the number of non-missing observations, the frequency of the observed endpoint as well as the observed proportion. The two-sided 95% CI of the observed proportion will be provided (when appropriate) using the exact method.

5.2.2. Analysis for Count Endpoints

For count variables such as ABR, AIR and bleeding episodes of specific types, the detailed analysis method will be discussed in Section 6. The median, the mean, interquartile range, minimum and maximum of the observed data will be reported in summary tables.

5.2.3. Analyses for Continuous Endpoints

The median, first quartile (Q1), third quartile (Q3), minimum, maximum, mean, standard deviation, 95% confidence interval (CI) of the observed value and the change from baseline, where appropriate, will be summarized in the tables.

5.2.4. Analyses for Categorical Endpoints

In general, counts and percentages will be presented for categorical variables.

5.3. Methods to Manage Missing Data

In general, missing data will not be imputed in this study, unless specified in Section 3, where individual endpoints are discussed.

6. ANALYSES AND SUMMARIES

6.1. Primary Endpoint(s)

6.1.1. ABR for Total Bleeds

6.1.1.1. Main Analysis

ABR_{total} will be analyzed using a repeated measures generalized linear model with negative binomial distribution and identity link function. Treatment (prophylaxis, or PF-06838435) and duration will be included in the model. Treatment will be a class factor in the model, duration is numeric and participant will be a random effect. Duration is the elapsed time in years of each treatment period. Duration is at least 0.5 for pre-PF-06838435 infusion prophylaxis which corresponds to six months. This period begins at enrollment of the lead-in study and ends on date of PF-06838435 infusion. Duration of PF-06838435 period is the observed time from Week 12 (Day 82) until cutoff for the specified analysis (e.g. 15 months for the primary analysis) or the date of study withdrawal or resumption of FIX infusion (whichever is earlier), minus any time that is predefined to be excluded.

- The Dosed population will be the primary analysis population. Analysis will be repeated for the Evaluable population if it is different from Dosed population.
- The mean ABR_{total} from Week 12 to Month 15 will be compared to the pre-infusion mean via the estimation of the mean difference and 95% CI. If the upper bound of the confidence interval of the difference of (ABR_{total} PF-06838435 ABR_{total} FIX prophylaxis) is smaller than 3.0, then statistical significance of the noninferiority claim would be demonstrated. An example of SAS code of such analysis is included in the Appendix 1.1. If noninferiority is demonstrated, further testing for superiority would be conducted after the primary analysis (assuming other endpoints within the

testing hierarchy are statistically significant), using the same method, except the margin would be modified to 0.

• The summary table will include two columns, for FIX prophylaxis and PF-06838435, respectively. The summary statistics in the table will include n, mean, median, Q1, Q3, range of the observed ABR_{total}, model derived mean ABR_{total} and 95% CI, estimated mean difference (model derived), and the 95% CI of the mean difference (model derived).

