The baseline ABR data for total bleeds will be calculated using the above formula and will be based on data collected in the Pre-Infusion Period while participants were on their respective usual care prophylaxis FIX replacement regimen. The baseline ABR will be annualized using the above formula counting bleeds and days in both the lead-in study (C0371004) and the screening period in C0371002 (from date of consent to date of study drug infusion).

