8. APPENDIX

Appendix 1. Statistical Methodology Details

Appendix 1.1. Example of SAS Code of Repeated Measure Additive Negative Binomial Regression Model:

proc genmod data=alldata;

class trt subjid;

model bleeds = years years*trt/link=identity dist=negbin noint;

repeated subject=subjid/Type=UN;

estimate 'diff' years*trt 1 -1/alpha=0.05; * adjust the alpha to a level if needed.

Estimate 'Prophy' years 1 years*trt 0 1;

estimate 'GTx' years 1 years*trt 1 0;

run;

Appendix 1.2. Example of SAS Code of Repeated Measure Negative Binomial Regression Model with log link:

```
proc genmod data=allbdyr; (offset=natural log of years)
    class trt subjid;
    model bleeds = trt /offset=lyears dist=negbin link=log alpha=0.05; * adjust the alpha to a
level if needed.
```

Repeated subject=subjid/ Type=UN; estimate 'log diff' trt 1 -1 / exp; ods output estimate=ci ratio;

run;

data ci_reduction;

set ci_ratio;

where Label= "Exp(log diff)";

Percent_reduction = 1- LbetaEstimate ;

```
Lower_bound = 1- LbetaUpperCL;
```

```
Upper_bound = 1- LbetaLowerCL;
```

Run;

Abbreviation	Term
AAV	Adeno-associated virus
ABR	annualized bleeding rate
ADA	anti-drug antibody
AE	adverse event
AESI	adverse event of special interest
AIR	annualized (FIX) infusion rate
ALT	alanine transaminase
APRI	AST to platelet ratio index
aPTT	activated partial thromboplastin time
AST	aspartate transaminase
BLoQ	Below limit of quantification
BUN	blood urea nitrogen
CDF	cumulative distribution functions
CI	confidence interval
COVID-19	Coronavirus disease 2019
CRF	case report form
CSR	clinical study report
DNA	deoxyribonucleic acid
DNase	deoxyribonuclease
ECG	electrocardiography
EHL	extended half-life
ELISPOT	enzyme-linked immunosorbent spot
EOS	end of study
EQ-5D-5L	EuroQoL, 5-dimensions, 5-levels
FIX	Factor IX
FIX:C	Factor IX: circulating
GGT	gamma-glutamyl transpeptidase
Haem-A-QoL	Haemophilia Quality of Life Questionnaire for Adults
HAL	Haemophilia Activities List
HBV	hepatitis B virus
HBcAb	hepatitis B core antibody
HBsAg	hepatitis B surface antigen
HCV	hepatitis C virus
hFIX-Padua	human factor IX-Padua
HIV	human immunodeficiency virus
HJHS	Hemophilia Joint Health Score
HLIQ	Hemophilia Life Impacts Questionnaire
IA	interim analysis
ICF	informed consent Form
IFNγ	interferon gamma

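### SAP 6.1.1.1 and 3.1.1 define pre-infusion exposure differently; any uncounted days between the lead-in study and consent would lower the modelled baseline ABR

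*SAP*

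**What the plan says.** SAP 3.1.1 annualises the baseline ABR by "counting bleeds and days in both the lead-in study (C0371004) and the screening period in C0371002", the latter running from consent to infusion. Days outside those two windows are in neither the numerator nor the denominator. SAP sections 2 and 5.2 fit this: both describe the pre-infusion data as what was collected in C0371004 plus what was collected before dosing in C0371002.

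SAP 6.1.1.1 describes the exposure variable for the primary model. "Duration is the elapsed time in years of each treatment period", and for the pre-infusion side "This period begins at enrollment of the lead-in study and ends on date of PF-06838435 infusion". The only other condition on that side is a floor: "Duration is at least 0.5 for pre-PF-06838435 infusion prophylaxis which corresponds to six months".

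The post-infusion side is worded differently: "Duration of PF-06838435 period is the observed time from Week 12 (Day 82) until cutoff for the specified analysis", ending earlier on withdrawal or resumption of FIX, "minus any time that is predefined to be excluded". That deduction appears only in the sentence on the PF-06838435 period.

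Appendix 1.1 shows how duration is used: "model bleeds = years years*trt/link=identity dist=negbin noint".

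**The concern.** One reading of pre-infusion time is a sum of two observed windows; the other is a single calendar span. They agree only if no days separate the end of C0371004 participation from C0371002 consent.

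The calendar span goes into the primary model. With an identity link and no intercept, the fitted rate is in effect bleeds per year of stated duration, so extra years without counted bleeds lower it directly. The primary summary table in 6.1.1.1 shows the observed ABR and the model-derived ABR together, and the two could then rest on different denominators with nothing to alert the reader.

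At stake are the accuracy of the estimated pre-to-post difference and the superiority tests on ABR. SAP 6.2.1 applies the same method to ABR for treated bleeds. In SAP Table 2 both ABR superiority tests come before the two patient-reported outcome tests and the final Hochberg group, so failing either one stops everything after it.

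**Working it through.** **1. Can there be days between the two windows?** The relevant text, side by side:

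- Protocol 5.1, criterion 1: at least six months of lead-in prophylaxis must precede consent. No maximum interval is given.
- Protocol 9.2 and SAP 2.2: participants who complete the lead-in are screened. No interval is given.
- Protocol 8.1.1: the C0371002 eDiary is issued at Visit 1.
- Protocol 5.4: screen failures may be rescreened under a new consent and a new participant number, and the minimum screen-failure data listed there do not include bleeds.

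A gap is therefore possible, most plausibly after rescreening. No text says that one occurred, how long it was, or that bleeds in it went unrecorded.

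**2. Dilution for an affected participant.** Inputs: a true pre-infusion rate of 5.0 per year (Protocol 9.2); 183 lead-in days (assumed, the six-month minimum) or 365 (assumed); and 42 days of screening and baseline (Protocol 1.3, from Week -6). Gap lengths are assumed.

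Modelled baseline = 5.0 × observed days ÷ (observed days + gap days)

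| Observed days | Gap 0 | Gap 30 | Gap 90 |
|---|---|---|---|
| 183 + 42 = 225 | 5.00 | 5 × 225/255 = 4.41 (-11.8%) | 5 × 225/315 = 3.57 (-28.6%) |
| 365 + 42 = 407 | 5.00 | 5 × 407/437 = 4.66 (-6.9%) | 5 × 407/497 = 4.10 (-18.1%) |

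With no gap the definitions agree, apart from the plus-one-day convention in the 3.1.1 formula.

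**3. Group mean.** If all 40 participants had a 90-day gap (225 observed days), the mean would shift by 5.00 - 3.57 = 1.43. If 10% did (an assumption), the shift would be about 0.10 × 1.43 = 0.14. The per-participant figures must therefore not be set directly against the margin of 3.0, which applies to the group difference.

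**4. The plan's power figure.** Protocol 9.2 states at least 90% power for non-inferiority with N = 40, one-sided 0.025, margin 3.0 and rates of 5.0 and 1.5. I used a Wald approximation, with k the dispersion:

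SE² = [5.0/t₀ + 25k + 1.5/t₁ + 2.25k] ÷ 40

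Power = Φ((3.0 + 3.5)/SE - 1.96)

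Here t₁ = (469 - 82 + 1)/365.25 = 1.062 years, t₀ = 0.5 to 1.0 years, and within-participant correlation is zero. Power exceeds 99.9% at k ≤ 1 and is about 99.9% at k = 2, 96-97% at k = 4 and 87-88% at k = 6. The stated figure is consistent with k up to somewhere between 4 and 6. It cannot be reproduced exactly, because neither k nor the correlation is given.

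**5. Effect of a gap on the tests.** Take 225 observed days (t₀ = 225/365.25 = 0.616), zero correlation, and the gap applied to every participant, which is the worst case. The baseline rate is multiplied by f = 225/(225 + gap) and its variance by f². For example, at k = 1 with a 30-day gap, SE = √[(0.7785 × 33.12 + 3.66)/40] = 0.858, the difference is 1.5 - 4.41 = -2.91, and superiority power is Φ(2.91/0.858 - 1.96) = 92%.

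| Gap | Expected difference | Superiority power, k = 1 | Superiority power, k = 2 |
|---|---|---|---|
| 0 days | -3.50 | 95% | 79% |
| 30 days | -2.91 | 92% | 73% |
| 90 days | -2.07 | 82% | 59% |

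Non-inferiority power is essentially unchanged, at or above 99.9% in all six cells. At the non-inferiority boundary (true rates 8 after and 5 before), a 30-day gap lowers the one-sided type I error from 0.025 to 0.010 (k = 1) or 0.013 (k = 2).

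**6. Sensitivity analyses (SAP 6.1.1.2).** Analysis 1 uses C0371004 alone and should avoid the gap. Analysis 2 uses the latest six months before infusion and, if taken as calendar time, could be diluted more: 30/183 = 16% for a 30-day gap, against 11.8% above.

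**The case against.** A reader might infer that the primary model does count unobserved days and that its baseline ABR is biased down. The documents do not support that. They show neither a gap nor a loss of bleed capture, and the lead-in protocol, which would settle the matter, is not among them. Some text points towards a direct handover: Protocol 8.3.1 sends new adverse events after lead-in completion to this study's process, which starts at consent, and those rules meet without a hole only if consent comes no later than lead-in completion.

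The pause in dosing mentioned in SAP 6.7 is also weak evidence. It concerned dosing, not consent or data collection. A participant held in an extended screening or baseline period already has the eDiary, and those days count under both definitions.

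It can also be said that 6.1.1.1 is shorthand for the Pre-Infusion Period defined elsewhere in the SAP, that any bias is conservative, and that sensitivity analysis 1 would reveal a material effect.

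Most of this stands: the bias is conditional, its size is unknown, and the primary conclusion is safe. What does not stand is the shorthand reading as a reason to leave the text alone. Section 6.1.1.1 specifies elapsed time for the pre-infusion side and writes its deduction only for the post-infusion side, so a programmer following it literally would use the calendar span.

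For AIR and FIX consumption no contradiction is shown. SAP 3.2.2 simply lacks the clarification about days in both studies that 3.1.1 gives.

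**Conclusion.** The SAP gives two definitions of pre-infusion exposure, and the one written for the primary model gives a wrong denominator whenever uncounted days lie between the two studies. Whether any do is not known from the documents.

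Under the assumed gaps of 30 to 90 days, an affected participant's baseline of 5.0 falls to between 4.66 and 3.57, depending on observed time. The group shift scales with the share affected. The direction is against the product, so the non-inferiority conclusion is not threatened. The cost is an understated reduction in bleeding and, if gaps were common, lower superiority power: from 95% to 82% at k = 1 in the worst case of a 90-day gap in everyone. Those power figures rest on assumed dispersion, zero within-participant correlation and the planning rates.

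That the bias is conservative does not make the estimated difference right, and the exposure variable of a primary model should have only one reading.

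**What to change.** In SAP 6.1.1.1, replace the calendar-span sentence with a definition identical to 3.1.1: pre-infusion duration is the sum of days under bleed collection in C0371004 and days from C0371002 consent to infusion, each calendar day counted once. State that:

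- the same exposure applies to ABR for treated bleeds (SAP 6.2.1);
- sensitivity analysis 2 in SAP 6.1.1.2, and its counterpart in 6.2.1, use days under bleed collection within the six-month window;
- for consistency, the baseline denominators for AIR and FIX consumption (SAP 3.2.2 and 3.2.4) use the same days.

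The cost is one sentence plus cross-references. It needs no new assessments, only each participant's lead-in start and end dates, consent date and infusion date; availability of the lead-in end date should be confirmed against the C0371004 data. If no participant has a gap, the results do not change beyond the one-day convention.
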